9.2. Data Management

The University of Washington will have the overall responsibility of this project and will serve as the Data Coordinating Center. As the Data Coordinating Center, UW will create the source documents for the study and be responsible for creating and managing the web-based, password-protected database. Any paper copies of the survey responses will be maintained in locked files in a locked room.

Participants will enter responses to the questionnaires directly into a UW Web-based program (REDCap). In case of technical difficulty with computer access to the REDCap website, participants will complete paper source documents. In order to ensure that surveys are being completed only by eligible participants, patients will be sent unique survey links that are connected to their email address. Therefore, if patients share the survey link with others, they can be contacted if there are multiple survey responses connected to their email address.

Case Report Forms (CRFs) will be de-identified, with only the participant study ID number, and entered into REDCap, a web-based, password-protected database managed by UW. CF centers will have access to a separate passwordprotected database that links the participant survey ID number with the name and birthdate of the participant, so that the selected CF center that is providing EMR data can complete the CRF with their institution's EMR.

The self-respondent contraception and reproductive history questionnaire will be entered into a separate REDCap database from the CRF information entered by the respective CF centers.

The UW will create a webpage for the study where CF centers can log in and view real-time, prepared reports that show response rates for patients at their CF center.

UW will send the CFFPR a list of participants and their birthdates, and CFFPR ID number. The CFF will provide UW with their CFFPR ID and requested registry data in Excel format. The UW will assign a central ID number for each participant, so that data from each of the databases can be connected for analysis.

9.3. Statistical Methods

Because this is a retrospective cohort study, we are most interested in determining whether this exposure (to hormonal contraception) is associated with our primary outcome (counting the number of pulmonary exacerbations requiring additional IV in a given year) and/or our secondary outcomes (new respiratory microbiology, liver disease/non-cirrhosis, gallstone, requiring surgery/procedure, improved BMI, incidence of VTE, osteoporosis and fragile bone fracture). Women on hormonal contraception will be compared to the primary control group of women on non-hormonal contraception. We will also compare to women on no contraception, as the secondary control group. We will exclude persons with these existing diagnosis at the start of the follow up period for outcome data (January 1, 2010). Within this objective we will be able to calculate incidence rates, relative risks and confidence intervals. We will use Poisson regression to calculate progestin-only and combined hormonal method to non-hormonal method pulmonary exacerbation rate ratios and 95% confidence intervals. This allows for adjustment of follow-up time of each individual.

(Objective 1a): We will evaluate lab values over time (ppFEV1%, serum AST, ALT, alkaline phosphatase) to determine if trends between hormonal contraceptive users and non-hormonal contraceptive users differ. See Table 5 for confounders and covariates that we will use to adjust for the primary and secondary outcomes.

We will model ppFEV1 via generalized estimating equations (GEE), allowing for correlation within a subject, and compare via a fixed effect for exposure. Among women who change or stop contraception, we will estimate and compare within-participant difference in outcomes via the model (if numbers allow). We will censor women who switch method types or become pregnant, and for 6 months post pregnancy, for the primary analysis and subsequently follow them to leverage within-patient data and analyze changes in pulmonary status and contraception. Presence of respiratory microbiology will be estimated longitudinally via GEE with a logit link function. Graphic displays and summary statistics will be used; all *p* values will be two-sided.

We will assess the strength of agreement between CFFPR reported data on osteoporosis, osteopenia and bone fracture compared to gold standard clinic DXA scan T-scores. We calculate the percent overall level of agreement between the CFFPR and clinical BMD scores using Cohen's kappa statistic calculation. Level of absolute agreement represents the proportion of participants for whom the CFFPR and clinic DXA scan T-score were correct. We will also report on proportion of scores entered within the year or year after DXA scan was completed, versus scores entered 3-5 years after DXA scan completed.

Missing Data

We will plan to impute missing data as our primary analysis. Should we discover large amounts of missing data, we will perform a sensitivity analysis excluding women with missing data to explore how findings differ from those without missing data.

Computer Facilities

Appropriate computer facilities are readily available for data analysis. REDCap will be used for entry and preparation of data for statistical analysis. Statistical analysis will be performed using STATA 12.

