7.5. Outcomes (include DAG diagrams to show relationships between exposure and outcomes)

Table 5: Outcomes and associated confounders and covariates

Exposure of interest	Outcome	Confounders/Covariates	Rationale
Combined	Pulmonary outcomes	Smoking	Affects lung function
hormonal contraception (CHC)	 Annual pulmonary exacerbation rate (PEx) (defined as episodes requiring intravenous 	Insurance status (reflection of SES)	Will be used as socioeconomic indicator. Less access to meds may mean less
&	antibiotic use at home or in		compliance
Progestin-only	hospital)Absolute change in FEV1 (in	Age	Lung function worsens as one ages
contraception	liters) Prevalence of micro-organism (defined as 1 or greater sputum	Education (reflection of SES)	Affects contraceptive knowledge decision making
	culture within a 12-month period)P. aeruginosa	ВМІ	Associated with better or worse health status in general

Exposure of interest	Outcome	Confounders/Covariates	Rationale
	 MDR P. aeruginosa Staph aureus 	Exercise	May reduce pulmonary exacerbation rates
	MSSA MRSA	CF genotype class	Associated with severity of disease
	Secondary infections: • Burkholderia cepacia	CFTR modulator treatment	Likely preserves pulmonary decline
	 Burkholderia cenocepacia Mycobacterial species –includes M. tuberculosis and NTM species 	Comorbidity with CFRD (defined as requiring chronic insulin therapy) (11)	Associated with worse disease (reduced immunity)
		Length of hormonal contraceptive use (person-year of exposure)	
	Venous/arterial thromboembolism (VTE)	BMI ≥ 30	
	 Noted on self-respondent survey (defined as blood clot requiring anticoagulation treatment) 	Age > 35 years PMHx for thrombophilia Arterial/venous lines or ports Pmhx cancer Smoking	
	Liver outcomes	BMI	Obesity contributes to
	 Liver disease, non-cirrhosis Gallstone, requiring surgery/procedure (defined as present or absent as 	Comorbidity with diabetes	liver dysfunction Associated with worse disease (reduced immunity)
	recorded in CFFPR)	Hepatitis	Risk factor for liver dysfunction
		CF genotype class Length of hormonal contraceptive use (person-year of exposure)	
	 Serum ALT, GGT (meets criteria if hepatic transaminases and GGT levels exceed upper limit of normal on at least 3 consecutive occasions over 12-month period) (12) 		Will track meeting criteria annually over time
	CF-related diabetes		
	 Serum ogtt trends New onset insulin resistance or diabetes (defined as 		

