9.1.3. Patient Surveys

Table 10: Information in online, self-respondent surveys

Survey O	nce Enrolled
• Demog	graphics: marital status, race/ethnicity, and education
	nedical history: ever smoked, ever had a blood clot requiring anticoagulation, # PICC lines placed, PORT in (dates)
Medic	ation history: ever taken CFTR modulator (with start and stop dates)
-	al history: Tubal ligation, hysteroscopic sterilization, hysterectomy, bilateral oophorectomy, other operation as made it impossible to get pregnant
• Menst	rual history: menarche, regularity of menstruation, menopause
• Contra	aception questionnaire
•	Questions regarding types of contraception used since 2008, start and stop dates of each method or age at first/last use. Questions are based off of the National Survey of Family Growth (NSFG)
• Pregna	ancy history questionnaire

- - Includes number of pregnancies in lifetime, year(s) pregnant, outcome of pregnancy, whether pregnancy was planned or not
 - Additional questions to include for funded study ([name] and [name]): times visited CF center during pregnancy and type of provider who cared for participant during pregnancy, ART

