 - Was the patient started on treatment for NTM

VII. COMPLICATIONS

- CF related diabetes encounter level
 - o CFRD Status
 - Chronic renal insufficiency
 - Chronic renal failure requiring dialysis
- Liver disease encounter level
 - o Gall stones
 - Gall stones, requiring surgery/procedure
 - Liver disease, cirrhosis
 - Acute hepatitis
 - Acute hepatitis infectious
 - Acute hepatitis non-infectious
 - Acute hepatitis unknown
 - Liver disease, non-cirrhosis
 - Hepatic Steatosis
 - Liver disease, other Acute liver failure
 - Other complications encounter level
 - Bone fracture
 - o Osteopenia
 - Osteoporosis
 - Cancer confirmed by histology

VIII. CARE EPISODES (HOSPITALIZATIONS/HOME IV)

- Care episodes
 - Start date for care episode [PHI]
 - End date for care episode [PHI]
 - # home IV nights with reason pulmonary exacerbation
 - # hospitalization nights with reason pulmonary exacerbation
- Care episodes summarized by calendar year
 - Total # pulmonary exacerbations treated by IV antibiotics
 - # nights in hospital for pulmonary exacerbations
 - # nights on home IV for pulmonary exacerbations
 - o Total # pulmonary exacerbation treated by IV antibiotics (incl unknown)
 - # nights hospital for pulmonary exacerbation (incl unknown)
 - o # nights home IV for pulmonary exacerbation (incl unknown)

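### The primary outcome is a yearly count, but methods start, stop and are censored within years; section 9.3 gives no rule to align them, although dated IV episodes are requested

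*Combined protocol and SAP*

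**What the plan says.** **Outcome.** Section 9.3 gives the primary outcome as "counting the number of pulmonary exacerbations requiring additional IV in a given year". Table 5 in section 7.5 lists it as "Annual pulmonary exacerbation rate (PEx" and limits it to episodes treated with intravenous antibiotics.

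**Exposure timing.** Table 10 in section 9.1.3 collects "start and stop dates of each method or age at first/last use". For pregnancies the survey asks only for the year, and the registry records only whether the patient was pregnant in the reporting year (Appendix, section I).

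**Person-time and censoring.** Section 9.3 says of the Poisson model: "This allows for adjustment of follow-up time of each individual". It then says: "We will censor women who switch method types or become pregnant, and for 6 months post pregnancy, for the primary analysis". Table 5 also lists duration of hormonal use in person-years as a covariate.

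**Event data.** Appendix section VIII requests dates for each care episode ("Start date for care episode [PHI", with a matching end date). It also requests a calendar-year summary, "Total # pulmonary exacerbations treated by IV antibiotics".

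The plan does not say which of these two event variables enters the primary model. It also does not say how a partly exposed year is labelled, or whether censoring takes effect on the exact date or at year end.

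**The concern.** The outcome is expressed per year, while the exposure and the plan's own censoring rule work on a finer scale. In a year when a woman starts or stops a method, a whole-year count mixes exacerbations that occurred on the method with others that did not. A window of six months after pregnancy cannot be removed from a calendar-year total: the year is either kept whole or dropped whole. The censoring text names switches of method type and pregnancy. It does not name starting a first method, or stopping to use none.

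The primary rate ratio is at stake. Events in transition years may be credited to the wrong group, and the labelling rule could be chosen after the linked data have been seen.

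**Working it through.** **Inputs from the documents.** Baseline rate 0.8 exacerbations per year and planning rate ratio 0.70 (section 7.7), so 0.8 x 0.70 = 0.56 per year on hormonal use. Outcome follow-up starts on 1 January 2010 (section 9.3). The plan gives no figure for misattribution, so there is none to reproduce.

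**Assumptions.** The documents give no spell lengths, switching rates or labelling rule. These are varied below.

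**Step 1: one transition year.** A woman starts a hormonal method on 1 July.
- Expected events in the year: 0.5 x 0.8 + 0.5 x 0.56 = 0.40 + 0.28 = 0.68.
- Correct on-method rate: 0.28 / 0.5 = 0.56, a ratio to 0.8 of 0.70.
- Whole year labelled hormonal: 0.68 / 1 = 0.68, ratio 0.68 / 0.8 = 0.85.
- Whole-year count over on-method time only: 0.68 / 0.5 = 1.36, ratio 1.36 / 0.8 = 1.70.

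The follow-up offset adjusts the denominator. It does not take the off-method events out of a yearly numerator, and combining the two can make the mismatch worse.

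**Step 2: two groups.** If a share q of person-time carries the wrong label equally in both groups:

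RR seen = [(1 - q) x 0.70 + q] / [(1 - q) + q x 0.70]

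- q = 2.5%: 0.7075 / 0.9925 = 0.713
- q = 5%: 0.715 / 0.985 = 0.726
- q = 10%: 0.73 / 0.97 = 0.753

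**Step 3: from spell length to rate ratio.** Alternating hormonal and non-hormonal spells, exponential with mean D years, were simulated over 9 calendar years with whole-year labels and a true rate ratio of 0.70.

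| Mean spell D | Years containing a change | Majority of year | Any hormonal use | Method on 1 January |
|---|---|---|---|---|
| 1 year | 63% | 0.79 | 0.82 | 0.86 |
| 2 years | 39% | 0.75 | 0.78 | 0.80 |
| 4 years | 22% | 0.73 | 0.75 | 0.76 |
| 8 years | 11-12% | 0.72 | 0.73 | 0.73 |

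Censoring at the first switch but keeping the whole count of the switch year gave nearly the same values. Exact-date censoring with dated episodes leaves 0.70.

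**Step 4: check by hand.** Under the 1 January rule the mislabelled share is q = 1/2 - (D/4) x (1 - exp(-2/D)).
- D = 2: q = 0.5 - 0.5 x 0.632 = 0.184, so RR = (0.816 x 0.70 + 0.184) / (0.816 + 0.184 x 0.70) = 0.755 / 0.945 = 0.80.
- D = 8: q = 0.5 - 2 x 0.221 = 0.058, so RR = (0.942 x 0.70 + 0.058) / (0.942 + 0.058 x 0.70) = 0.717 / 0.983 = 0.73.

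Both agree with the table.

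**The case against.** The strongest reply is that the plan never says the calendar-year total is the analysis variable. An annual rate can simply mean events per person-year. Dated episodes are requested beside the totals, section 9.3 adjusts for individual follow-up time, and switchers and pregnancies are censored in the primary analysis. If censoring is done by date and events are dated, the problem largely disappears. This stands. It means misattribution is a risk the plan leaves open, and a reader should not infer that the rate ratio will be diluted.

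Three further points also stand.
- The direction is not assured. Bias toward 1 needs non-differential mislabelling. If worsening health prompts a woman to stop or change a method, or once there are more than two groups (combined, progestin-only, non-hormonal, none), it can go either way.
- A reader might infer a specific loss of power. Section 7.7 does not state the years of follow-up per woman, and spells of several years contribute several person-years, so no such figure can be derived.
- A reader might infer that asking for age at first and last use merges separate spells into one. Table 10 is a one-line summary that lists dates first, and the questionnaire itself is not shown.

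The reply does not close the gap. The offset leaves the yearly numerator untouched, the censoring text omits starts and stops to no method, and the six-month exclusion needs timing finer than a year. Dated episodes alone are not a full remedy either, because some method use and all survey pregnancies may be known only to the year.

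**Conclusion.** The concern holds as a gap in the definition of the primary analysis. The yearly outcome does not fit within-year exposure or the plan's own censoring rule, and dated episodes that would support a better definition are already requested.

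If calendar-year totals were used, a true rate ratio of 0.70 would appear as about 0.72-0.73 with mean spells of 8 years and 0.75-0.80 with mean spells of 2 years. These figures rest on assumed spell lengths, three assumed labelling rules, two groups and non-differential mislabelling. The effect is therefore small for long-term users and material for women who change often. The documents do not establish that dilution will occur, its direction in every comparison, or any loss of power.

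**What to change.** 1. In section 9.3, define the primary outcome as the number of IV-treated exacerbation episodes by care-episode start date, each assigned to the method in use on that date.
2. Use person-time split at method start, method stop and censoring dates as the Poisson offset. State explicitly how first starts and stops to no method are handled. Keep the calendar-year totals for description only.
3. State one rule for method use or pregnancy known only to the year, for example mid-year assignment, with a sensitivity analysis that drops transition years.
4. In the survey, record start and stop month and year for each separate spell where the participant can recall them, instead of only age at first and last use. Section 7.0 already provides for revising the questionnaire after pre-testing.

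The event variables are already in the registry request. The cost is some extra programming and a slightly longer survey.

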4.2. Secondary Study Objectives/Endpoints

- To assess the association of hormonal contraceptive use on trends in lung function (FEV1) over time, compared to non-hormonal contraceptive users (primary control) and non-contraceptive users (secondary control).
- To assess the association of hormonal contraceptive use on the incidence of venous or arterial thromboembolism.
- To assess the association of hormonal contraceptive use on prevalence of liver dysfunction, defined as gallstones (requiring surgery), hepatic steatosis, hepatic cirrhosis, and/or incidence of increased liver enzyme test values (ALT/GGT). Increased liver enzymes is defined as exceeding upper limit of normal on at least 3 occasions over 12-month period.
- To assess the association of hormonal contraceptive use on serum glucose trends, incidence of insulin resistance or time to CF-related diabetes (requiring insulin treatment).

- To assess association of hormonal contraceptive use on nutritional status through the evaluation of BMI trends.
- To validate bone health information in CFFPR with chart data obtained from one CF center (limited due to need for data use agreements between institutions for EMR data).
- To determine if those using hormonal contraception while using CFTR modulators report higher rates of unintended pregnancy compared to those taking non-hormonal contraception.
- To assess proportion of mucoid *P. aeruginosa*, in patients who are *P. aeruginosa* positive, among hormonal contraception users compared to non-hormonal contraceptive users.

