7.2. Eligibility Criteria

The study population will be women with CF who have used any form of contraception for protection against pregnancy or for treatment of dysmenorrhea, pelvic pain, abnormally heavy or prolonged menstrual bleeding, excessive uterine bleeding, endometriosis, acne, or amenorrhea.

Table 4: Full study inclusion and exclusion criteria

Inclusion Criteria
Females ages ≥ 18 and < 46 years at enrollment
Confirmed patients at one of the 10 participating CF centers (has been seen at least one time for a face-to-face
office visit at the CF center in the last 2 years)
CFFPR participant (noted as having a CFFPR ID number)
Has internet access
Has a functioning email addresses or may create a functioning email address at enrollment
Willing to consent to obtain request of their identified data from CFFPR
Willing to consent to their CF center to provide data related to contraceptive medication and DXA scan test results
as far back as 2013 in clinic EMR
Exclusion Criteria
Not in CFFPR
Non-functioning email address
History of organ transplant
Participant in pre-test phase of this study

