8.0. Methods: Assignment of interventions

8.1. Allocation

Participants will belong to a group based on their choice of contraception. Women with CF will be allocated to hormonal group (intervention), non-hormonal groups (control), and never used contraception.

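### Existing diagnoses are judged at 1 January 2010 for every woman and at-risk time is not tied to method start, so a diagnosis before a first method can count as incident in that method's group

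*Combined protocol and SAP*

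**What the plan says.** Section 9.3 lists diagnosis-type secondary outcomes, among them non-cirrhotic liver disease, gallstones needing a procedure and thromboembolism. It promises incidence rates and relative risks, and sets the disease-free check as follows: "We will exclude persons with these existing diagnosis at the start of the follow up period for outcome data (January 1, 2010". Section 8.1 assigns by woman: "Women with CF will be allocated to hormonal group (intervention), non-hormonal groups (control), and never used contraception".

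Methods begin at different times. The survey (9.1.3, Table 10) asks for "start and stop dates of each method or age at first/last use", going back to 2008.

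Four other places bear on how time is handled:

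- 9.3, exit rule: "We will censor women who switch method types or become pregnant".
- 9.3, in the paragraph on the ppFEV1 model: "Among women who change or stop contraception, we will estimate and compare within-participant difference in outcomes via the model (if numbers allow".
- 7.5, Table 5, as a covariate: "Length of hormonal contraceptive use (person-year of exposure".
- 7.2: "The study population will be women with CF who have used any form of contraception".

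None of these says when a woman's time at risk in a method group begins, or where time and events between 1 January 2010 and a later method start belong. The liver objective in 4.2 is worded partly as prevalence: "To assess the association of hormonal contraceptive use on prevalence of liver dysfunction".

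**The concern.** An incident diagnosis can be credited to an exposure only if it follows that exposure. With one disease-free date for all women and groups defined per woman, a woman who had a gallstone procedure in 2013 and began her first hormonal method in 2016 passes the 2010 check, belongs to the hormonal group, and supplies an event to it. Her unexposed years from 2010 to 2016 also enter that group's denominator.

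This touches the study's safety questions. Section 3.0 hypothesises more gallbladder disease, raised liver enzymes or more thromboembolism with estrogen-containing oral methods. If starting a method is unrelated to earlier diagnosis, mixing in unexposed time and events pulls a real harm towards no effect. If an earlier diagnosis makes starting less or more likely, the ratio can move either way.

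**Working it through.** **1. Is there an entry rule anywhere?** The passages, read together:

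- The exclusion in 9.3 is a calendar date, not a date relative to method start.
- The switch rule in 9.3 ends follow-up. It does not begin it, and it does not clearly cover a move from no method to a first method.
- Person-years of exposure in Table 5 is a covariate, not a rule for allocating time.
- The within-participant comparison is conditional on numbers.
- The Poisson model in 9.3 adjusts for each woman's follow-up time without saying when that time starts.

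No index date at method start is stated. The plan gives no figure on this point to reproduce.

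**2. How common could late first starts be?** Inputs:

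- Pre-testing ends in July 2020 (7.0) and enrolment lasts about 15 months (7.1.1). Enrolment is therefore taken as 1 August 2020 to 31 October 2021, which is 10.58 to 11.83 years after 1 January 2010.
- Table 3: 383 women aged 18-35 and 192 aged 36-45, 575 in all. Ages are assumed uniform within bands.
- Age at sexual debut 16-17 (7.1), used here as an assumed age at method start.

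A woman was below 16 on 1 January 2010 if her enrolment age is under 26.58 (27.83 for the latest enrolment), and below 17 if it is under 27.58 (28.83).

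- Below 16: 383 × (26.58 − 18)/18 = 183, to 383 × (27.83 − 18)/18 = 209.
- Below 17: 383 × (27.58 − 18)/18 = 204, to 383 × (28.83 − 18)/18 = 230.

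Overall that is 183 to 230 of 575, or 32% to 40%. The older band contributes none.

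**3. Illustrative size when starting is independent of diagnosis.** The window W is 9 or 10 years (2010 to 2018 or 2019, section 5.0). Assume a first-event hazard h before method start and R·h after it, with R = 2.0 and h = 0.005 to 0.02 per year. The comparator has hazard h and correctly classified time. All of a user's time to first event is credited to the method. For a start at time S:

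- E = 1 − exp(−hS − Rh(W − S))
- T = (1 − exp(−hS))/h + exp(−hS) × (1 − exp(−Rh(W − S)))/(Rh)
- Ratio seen = mean(E) / (h × mean(T)), which is roughly R − (R − 1)f, where f is the pre-use share of users' window time.

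If a fraction p of users start uniformly over the window and the rest are already users, f = p/2:

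| p | f | 2 − f | Ratio seen, full formula |
|---|---|---|---|
| 25% | 12.5% | 1.875 | 1.86-1.87 |
| 50% | 25% | 1.75 | 1.73-1.74 |
| all (upper bound) | 50% | 1.50 | 1.47-1.49 |

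**4. The same with the documents' ages.** Women below 16 or 17 on 1 January 2010 start at that age, and the others are taken as already using. Women who would start only after the window closes (up to 6.8%) are left out, because they are not users within it.

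- Low end (lag 10.58, start at 16, W = 10): starts are spread over 0 to 8.58 years, mean 4.29. f = 182.6 × 4.29/(575 × 10) = 13.6%.
- High end (lag 11.83, start at 17, W = 10): starts are spread over 0 to 10.83 years. Of 230.4 women, 212.7 start within the window, at a mean of 5 years, and 17.7 are left out. f = 212.7 × 5/(557.3 × 10) = 19.1%.

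Across the combinations, f is about 14-19% and a true 2.0 is seen as about 1.79-1.86.

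**5. What softens this.** All the pre-use time in step 4 falls before age 17, yet the model uses one hazard at all ages. If the hazard before 17 is lower, dilution is smaller. If it were zero and comparators had the same ages, events and time would shrink in step in both groups and the dilution would disappear.

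**The case against.** The strongest reply is that this is an unwritten rule, not a demonstrated error. Section 9.3 speaks of women on a method, allows for individual follow-up time, censors switches and plans within-participant comparisons. The survey collects start and stop dates, and 8.1 merely names groups. A population of ever-users (7.2) also suggests that time without contraception must come partly from women who use a method at other times. A careful analyst could assign time correctly from these data.

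Much of that stands. The harm depends on reading the groups as fixed per woman. Where the switch rule applies, a diagnosis before a switch stays with the earlier method, so the problem lies mainly with first starts from no method. But the hints do not amount to a rule, while the one explicit rule, the 2010 exclusion, points the other way.

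A reader might go further and infer that temporal order will certainly be wrong for these endpoints, or that a false protective or harmful effect of known size will result. The documents support neither. They say nothing on whether diagnosis affects starting. The primary control group also starts methods, so if its starts depend on earlier diagnosis in the same way, that bias shrinks or vanishes.

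**Conclusion.** The point holds as a defect in the stated rule for incident gallstone procedure, non-cirrhotic liver disease and thromboembolism: a diagnosis made before a first method can be credited to that method. It rests on the person-level reading and mainly on women going from no method to a first method after 1 January 2010.

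The figures are illustrations under assumed start patterns, a constant hazard and a correctly classified comparator. The age-based case (2.0 seen as about 1.79-1.86) is the one tied most closely to the documents, and it overstates dilution if hazards before age 17 are low. With starts that depend on diagnosis, the direction is unknown and no figure is warranted.

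A reader might also infer that the primary analysis is compromised. It is not on this ground: the exacerbation count, FEV1 and BMI trends and the GEE microbiology model do not rest on a first-diagnosis date. The liver endpoint is affected only where it is analysed as incidence. Section 9.3 names bone outcomes too, but the bone objective and hypothesis concern registry validation, so the point does not lean on them.

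**What to change.** In 9.3, for incident diagnoses:

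- Start at-risk time in a method group at the later of 1 January 2010 and method start.
- Require the woman to be free of the diagnosis at that date. For women already using a method on 1 January 2010, judge this from the first 2010 registry record, since registry data are requested only from 2010.
- Assign person-time and dated events to the method in use.
- Count pre-use time as no-contraception time only within the age range where method users also contribute time, and adjust for age. Adjustment alone cannot repair childhood years in which there are no users to compare.
- State how methods reported only by age at first or last use are placed in time. Add a sensitivity analysis for events whose order relative to method start is uncertain. The Appendix requests liver and gallstone entries at encounter level together with encounter dates, but these are recording dates, not onset dates.
- Confirm that the survey records the date of any blood clot, and add it if not. The Table 10 line does not make this clear.

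The cost is wording in 9.3, at most one survey date item, and programming to split person-time. Time credited to users falls by the pre-use share: 12.5%, 25% or 50% in the uniform illustrations, about 14-19% in the age-based one. That time was unexposed.
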